3. SYNOPSIS

Trial Title	Smartphone Screentime Reduction improves mental health: A randomized clinical trial				
Internal ref. no. (or short title)	EK GZ 67/2021-2024				
Trial registration	https://osf.io/a9k76				
Sponsor	N.a.				
Funder	N.a.				
Clinical Phase					
Trial Design	Two group, not blinded, randomized controlled trial with a follow up.				

Trial Participants	Healthy adults could participate if thes were 1) between 18 - 29 yo, 2) owning a smartphone and using it at least 3 h/d, and 3) no diagnosed or treated mental disorder, no ongoing psychotherapy or psychopharmaceutic therapy (self-report). Moderately elevated levels in mental health screening questionnaires were no exclusion criteria.			
Sample Size	With a small to medium effect size (Cohens d= 0.45; power .8, significance level < .05, icc = .05), significant results can be expected with a completed data set of minimum 40 people per group. Considering a drop-out rate of 20%, at least 50 people per group were recruited.			
Planned Trial Period	The total study period will be 12 weeks: Screening for eligibility, 10 days baseline phase, 3 weeks intervention, 6 weeks post intervention to follow-up			
Planned Recruitment period	Study protocol submission: August 20, 2023; Approval by Ethical committee October 23, 2023; Information on Social Media and notices at University; Registration November 8, 2023; Screening for Eligibility November 8-10, 2023 Objectives Outcome Measures Timepoint(s)			
Primary	 Depressive Symptoms Well-being Stress Sleep Quality 	 Patient Health Questionnaire (PHQ-9) World Health Organization wellbeing questionnaire (WHO-5) Perceived Stress Questionnaire (PSQ-20) Insomnia Severity Index (ISI) 		
Secondary	 Problematic Smartphone Use Disordered Eating Body Appreciation Anxiety 	 Smartphone Addiction Scale (SAS-SV) SCOFF BAS-2 GAD-7 		
Intervention(s) •	The intervention is reducing smartphone screen time <2/h for 3 weeks. Smartphone screen time will be assessed weekly in both groups using the smartphones' built-in screen time measurements. Weekly, participants will be asked to upload a screenshot from their screen time from the previous week.			

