5. OBJECTIVES AND OUTCOME MEASURES

Objective, Research Question, Procedure, and Design

Clinical Trial Protocol Template version 14.0

CONFIDENTIAL

© Copyright: The University of Oxford and Oxford University Hospitals NHS Foundation Trust 2018

The aim of the planned study is to reduce the screen time of healthy students in Austria over a period of 3 weeks and to investigate its impact on mental health.

Mental health indicators were evaluated in both groups at baseline, post-intervention, and at follow-up (t2). Participants will be informed weekly via App.

1. Main outcomes

Well-being (WHO-5): The validated German version of the World Health Organization well-being questionnaire (WHO-5) will be used.

Depressive symptoms (PHQ-9):Depressive symptoms will be assessed using the Patient Health Questionnaire (PHQ-9) in the validated German version.

Stress (PSQ-20): Stress will be assessed using the German version of the 20-item short-form of the Perceived Stress Questionnaire.

Sleep quality (ISI): Sleep quality will be assessed with the Insomnia Severity Index (ISI).

2. Additional outcomes

Problematic smartphone use (Smartphone Addiction Scale (SAS-SV)), anxiety symptoms (GAD-7), disordered eating (SCOFF), and Body Appreciation (BAS-2) will further be assessed.

Physical activity will be measured using a fitness tracker, as well as heart rate variability (HRV) and resting heart rate.

Objectives	Outcome Measures	Timepoint(s) of evaluation of this outcome measure (if applicable)
Depressive Symptoms (PHQ-9) Well-Being (WHO-5) Stress (PSQ 20) Sleep quality (ISI)	 Patient Health Questionnaire (PHQ-9) World Health Organization well-being questionnaire (WHO-5) Perceived Stress Questionnaire (PSQ-20) Insomnia Severity Index (ISI) 	At Baseline, post- intervention and at Follow-up.
 Problematic Smartphone Use 	 Smartphone Addiction Scale SCOFF BAS-2 GAD-7 	At Baseline, post- intervention and at Follow-up.

Disordered Eating	
 Body Appreciation 	
 Anxiety 	

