9. TRIAL INTERVENTIONS

Screen time (less than 2 hours per day) as well as social media use (less than 1 hour per day) should be reduced for a period of 3 weeks and the effects should be compared to a controlled group. A sample of N > 96 should be recruited through newsletter, notices and advertising on social media. The inclusion criteria are more than 3 hours of screen time per day, and no psychiatric illness for which they are being treated. After informing and signed the consent form, the participants have to download an App (ESMira®), which processes the whole study. The first step is to fill out sociodemographic data, smartphone usage and mental health questionnaires. After controlling for inclusion and exclusion criteria, ESMira will randomize into intervention (A) and controlled group (B). The participants in the intervention group (A) should continue their social media use and smartphone screen time unchanged for the first 10 days (Baseline.) After that (t1), the participants should limit their use of social media, such as Instagram, TikTok, Snapchat, Facebook, or similar sites to one hour per day and the complete screen time under two hours per day. To comply with that, participants should use the limiter function of there smartphone or download an additional app. Screen time of the smartphone and the social media use will be tracked automatically or via uploading a screenshot. At the end of the intervention (t2), the mental health questionnaires will be collected again. Afterwards there are no further tasks for the participants in the intervention group (A), screen time and social media use is possible again without restrictions. Screen time and social media use will be tracked until 3 month follow up (t3). During the study period participants will be asked to additionally wear a fitness tracker to measure daily movement as well as sleep behavior. The controls group (B) will be asked to continue their social media use and screen time unchanged to follow-up, after that the will be asked to fill out the mental health questionnaires again. After follow up, control group (B) will be offered to participate at intervention to keep drop outs and missing values low.

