11. STATISTIC ANALYSIS PLAN

We will use the statistic software IBM SPSS Statistics (IBM Corp., Armonk, NY, USA) to analyze the data. χ^2 -Test and independent samples tests will be used to examine differences at baseline (t0) regarding age, gender, smartphone screen time, physical activity per week, and mental health indicators between the control and the intervention group.

Clinical Trial Protocol Template version 14.0

CONFIDENTIAL

To examine the effect of reduced smartphone screen time on the mental health indicators, repeated measurements ANOVAs (rm-ANOVA) will be applied. The primary hypotheses focuses on the difference between t0 (baseline) and t1 (post-intervention) between control group and intervention group (between group effect). In a secondary analysis, the follow-up time point (t2) will also be included.

Group allocation (control vs. intervention) will be the between-group factor, time will be the within-group factor (t0, t1, t2). Furthermore, a sub-group analysis (rm-ANOVA) will be applied of those, who strictly adhered to the 2h smartphone screen time limit during all three weeks. In case of baseline group-differences in the mental health indicators, these variables will be added as a covariate in the rm-ANOVA. If the sphericity assumption will be violated, the Greenhouse-Geisser correction will be applied. In the post hoc tests, Bonferroni correction will be applied to adjust for multiple comparisons.

Missing values will be estimated with via maximum likelihood estimation.

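### Each primary outcome's baseline score should always be a covariate, not only when the arms happen to differ at baseline

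*Combined protocol and SAP*

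**What the plan says.** Section 11 (Statistic Analysis Plan) starts with tests between the arms at baseline, the questionnaire scores included: "independent samples tests will be used to examine differences at baseline (t0) regarding age, gender, smartphone screen time, physical activity per week, and mental health". The result decides the model: "In case of baseline group-differences in the mental health indicators, these variables will be added as a covariate in the rm-ANOVA". Nowhere in the document does the baseline score enter unconditionally. The default is a repeated-measures ANOVA with group as the between factor and time as the within factor.

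The primary contrast is worded "The primary hypotheses focuses on the difference between t0 (baseline) and t1 (post-intervention) between control group and intervention group (between group effect").

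Section 9 (Trial Interventions) gives the order of events. Once participants are in the app, "The first step is to fill out sociodemographic data, smartphone usage and mental health questionnaires"; the eligibility check and randomisation follow.

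The visit labels do not agree. In section 11, t1 is the post-intervention visit. In section 9, "At the end of the intervention (t2), the mental health questionnaires will be collected again". In section 5, "Mental health indicators were evaluated in both groups at baseline, post-intervention, and at follow-up (t2").

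**The concern.** In a randomised trial any baseline difference between the arms is due to chance. A significance test on it does not measure what makes a covariate worth having, which is how strongly it predicts the outcome. A baseline questionnaire score usually predicts the later score on the same questionnaire whether or not the arms happen to differ. A rule that waits for a difference therefore leaves the useful covariate out most of the time.

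The rule is also incomplete. It gives no threshold for a difference. It does not say whether a variable that differs enters only its own outcome's model or every model. The final primary model is therefore not known until the data have been seen.

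What is at stake is power, in a trial planned for only 40 completers per arm, and full pre-specification of the primary model.

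**Working it through.** **1. Inputs.** The synopsis gives 40 completers per arm and "Cohens d= 0.45; power .8, significance level < .05, icc = .05". Assumed here: a two-sided test, equal arms, the same unit SD at both visits, and a trigger of p < 0.05 on the outcome's own baseline. The documents state no baseline to post-intervention correlation r, so a range is shown.

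**2. The plan's own figure.** A plain two-sample comparison needs 2(1.960 + 0.842)² / 0.45² ≈ 78 per arm, not 40. Reading the ICC of 0.05 as the correlation between two repeated measures, the variance of their mean is (1 + 0.05)/2 = 0.525, and 0.525 × 77.5 ≈ 41 per arm. Noncentral-F formulas for a two-visit rm-ANOVA (f = 0.225) give 42 per arm for the group effect and 38 for the interaction. So 40 is roughly reproduced. However, the group-effect formulas need a difference of 0.45 averaged over both visits. If the arms are equal at baseline and differ by 0.45 afterwards, the average differs by only 0.225. The interaction formula has noncentrality f²·2N/(1−ρ), four times the change-score value d²N/{8(1−ρ)} at d = 0.45, so it implies a difference in change of 0.90. This is why the powers below fall short of 80%.

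**3. Variances.** With two visits, the group-by-time test is a t test on change scores.
- Change score: per-person variance 2(1 − r), 78 error df.
- ANCOVA: per-person variance (1 − r²), times 1 + 1/76 for estimating the slope, 77 error df.
- Ratio ANCOVA/change before the slope cost: (1 − r²)/{2(1 − r)} = (1 + r)/2.

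**4. Example, r = 0.5.** Change score: 0.45/√(1.00 × 2/40) = 2.01, power 51%. ANCOVA: 0.45/√(0.75 × 1.0132 × 2/40) = 2.31, power 63%.

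**5. Over the range.** Change-score and ANCOVA power are from the noncentral t distribution. The planned rule is simulated with 40,000 trials per cell.

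| r | (1+r)/2 | Change score | Planned rule | Always ANCOVA | n/arm for 80%: change v ANCOVA |
|---|---|---|---|---|---|
| 0.05 | 0.525 | 30% | 30% | 51% | 149 v 79 |
| 0.3 | 0.65 | 39% | 40% | 54% | 110 v 73 |
| 0.4 | 0.70 | 44% | 44% | 58% | 94 v 67 |
| 0.5 | 0.75 | 51% | 52% | 63% | 79 v 60 |
| 0.6 | 0.80 | 60% | 61% | 69% | 63 v 52 |
| 0.7 | 0.85 | 73% | 73% | 79% | 48 v 42 |
| 0.8 | 0.90 | 88% | 88% | 91% | 32 v 30 |
| 0.9 | 0.95 | 99% | 99% | 99% | 17 v 17 |

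The sample sizes include the slope cost. At 40 per arm, 80% power is reached from r ≈ 0.71 with ANCOVA and r ≈ 0.75 with change scores.

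**6. Break-even.** Setting (1 + r)/2 × (77/76) = 1 gives r = 2 × 76/77 − 1 ≈ 0.97. Above that, adjustment loses about 0.1 to 0.3 percentage points of power.

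**7. How the rule behaves.** It fires in about 5% of trials per outcome, so it recovers almost none of the gain. Across independent indicators, the chance that at least one fires is 1 − 0.95⁴ = 19% for the four primary ones and 1 − 0.95⁸ = 34% for all eight questionnaires. With an assumed correlation of 0.7 between indicators these are 13% and 19%. Simulated type I error of the rule is 3.7% (r = 0.05), 4.0% (0.3), 4.4% (0.5) and 4.8% (0.9).

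**8. The parenthesis in the primary contrast.** Read literally as the rm-ANOVA group main effect (difference 0.225, variance (1 + r)/2), power is 21% at r = 0.5 and 18% at r = 0.8.

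**The case against.** The strongest reply is that this is a choice between two valid estimators. Baseline already enters as a level of time, and the planned test is unbiased and slightly conservative. The gain rests wholly on an unknown r: 11 to 15 points at 0.3 to 0.5, but 6 at 0.7 and about 3 at 0.8. Adjustment does not by itself bring the trial to 80%. All of this stands, and it limits the weight of the point without removing it.

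Second, the power and type I figures belong to an assumed p < 0.05 trigger, not to a rule the plan states. That is correct. A trigger of p < 0.20 moves power at r = 0.5 only to about 53%. The assurance on false positives holds only for a rule applied mechanically. In a worst case, where the analyst chose freely between the two models, type I error would be about 7.7% (r = 0.3) to 6.2% (r = 0.9). The plan does not propose that, but its open wording does not exclude it.

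Third, the timing of baseline is less clear than section 9 suggests. The lay summary calls the ten days after randomisation the baseline, and section 11 does not tie t0 to a date. In an unblinded trial a score taken after allocation would be a poorer covariate. The fix must therefore name the pre-randomisation questionnaire.

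Fourth, the parenthetical phrase may simply mean a comparison between arms. That is a fair reading, and the low power in step 8 applies only to the literal one.

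**Conclusion.** The concern holds. Adjustment depends on chance imbalance, and always adjusting is more efficient at this sample size for any r from 0 to about 0.97, at the cost of one error degree of freedom (78 to 77). At 40 per arm and d = 0.45 the planned rule gives up about 15 percentage points of power at r = 0.3, 11 at 0.5, 6 at 0.7 and practically none at 0.9. If the synopsis ICC of 0.05 is meant as the repeated-measures correlation, the loss is about 20 points (30% v 51%).

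These sizes rest on the assumed r, a two-sided test, equal SDs and a p < 0.05 trigger. The harm is lost power and an incompletely specified primary model, not bias. The change should be made, but the trial is not invalid without it.

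**What to change.** For each primary outcome, define the primary analysis as the baseline-adjusted group difference at the visit ending the 3-week intervention. Estimate it by ANCOVA, or by the equivalent contrast from a mixed model, and always include that outcome's own questionnaire score from before randomisation as a covariate.

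- Delete baseline testing as a trigger for adjustment. Baseline values can still be described by arm.
- Replace the parenthesis in the primary hypothesis with: baseline-adjusted group difference at the post-intervention visit.
- Name visits in words, because the end of the intervention is t1 in section 11 but t2 in the lay summary and section 9, while t2 means follow-up in sections 5 and 11.

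The cost is SAP wording and one degree of freedom per model; the data and software stay the same. The change does not replace a review of the sample size, since 80% power at 40 per arm still requires r of about 0.71 or more.

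### Section 11 gives no success rule for four unranked primary outcomes, so error control for a general claim of better mental health is left undefined

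*Combined protocol and SAP*

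**What the plan says.** The primary row of the Synopsis (Section 3) lists "Depressive Symptoms Well-being Stress Sleep Quality", measured by PHQ-9, WHO-5, PSQ-20 and ISI. Sections 5 and 8.6 list the same four scales as main outcomes. None of these places ranks them.

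Section 11 analyses the mental health indicators with repeated-measures ANOVAs and defines the primary contrast by time and group only: "The primary hypotheses focuses on the difference between t0 (baseline) and t1 (post-intervention) between control group and intervention group (between group effect". Follow-up comes later: "In a secondary analysis, the follow-up time point (t2) will also be included". The one sentence on multiplicity is "In the post hoc tests, Bonferroni correction will be applied to adjust for multiple comparisons".

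The only significance level is in the Synopsis sample-size text: "Cohens d= 0.45; power .8, significance level < .05, icc = .05". The trial title carries a general claim, "Smartphone Screentime Reduction improves mental health", tied to no scale. The hypothesis in Section 2 names stress, depressive symptoms and sleep quality as particular examples joined by a conjunction. It leaves out well-being and asks for improvement both against control and against baseline.

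**The concern.** With four primary tests, the error rate of the trial's conclusion depends on the rule that turns four results into one statement. The plan gives no such rule: no lead scale, no testing order, no split of alpha and no number of scales that must succeed. The Bonferroni sentence follows the one on sphericity and is limited to post hoc tests, so it most naturally means pairwise comparisons within an ANOVA. The primary contrast is not post hoc.

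Several rules therefore remain open: any one scale, all scales, or a separate claim per scale. They differ widely in false-positive rate and power, and without a written rule the choice can be made after the results are seen.

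**Working it through.** **Inputs from the documents.** Four primary outcomes, alpha .05, d = .45, power .80, icc .05, 40 completers per group.

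**Assumptions.** Tests are two-sided: an F test of group by time over two time points has no direction, but the plan does not state sidedness. Correlations between the four outcomes are not given and are shown over a range, equal for all pairs. For power, d = .45 holds on every scale.

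**The plan's own figure.** Comparing group means of two measures with correlation .05, the variance factor is (1 + .05)/2 = .525. Completers per group = 2 × (1.960 + 0.842)² × .525 / .45² = 40.7, close to the stated 40.

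**Any one of four scales suffices, no true effect on any.** At correlation 0:
- Two-sided error: 1 − .95⁴ = 18.5%.
- False improvement on at least one scale: 1 − .975⁴ = 9.6%.

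For correlated outcomes these come from numerical integration of a four-variate normal. The last column is the first Holm step (.05/4 = .0125 per scale), which fixes the family-wise error when no effect is real.

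| Outcome correlation | Two-sided family-wise error | False improvement on any scale | Ratio to 2.5% | Two-sided family-wise error with Holm |
|---|---|---|---|---|
| 0 | 18.5% | 9.6% | 3.9 | 4.9% |
| .3 | 17.4% | 8.7% | 3.5 | 4.7% |
| .5 | 15.6% | 7.8% | 3.1 | 4.3% |
| .7 | 13.0% | 6.5% | 2.6 | 3.7% |

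False improvement with Holm is about 2.5% at correlation 0 (1 − .99375⁴) and 1.8% at .7. It should be compared with the third column, not with the two-sided rates.

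**Other rules the text leaves open.**
- All four must succeed: no inflation. At outcome correlation .5, power on the formula above is about 54%.
- Bonferroni meant across the four outcomes: false improvement 2.5% or less.
- Bonferroni read as .05/3 on each scale, because Section 11 also lists three time points: two-sided error 1 − (1 − .05/3)⁴ = 6.5% at correlation 0 and 4.8% at .7.
- Each scale must also improve on its own baseline, with no true change in either group: any-scale false improvement is a little over 3% at correlation 0 and about 2.5% at .7. A general trend towards improvement over time would push it back up.
- Four separate claims: 5% two-sided error for each.

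**Power cost of Holm, same formula, 40 per group.** The expected test statistic is .45 / √(2 × .525/40) = 2.78. Power at .05 is Φ(2.78 − 1.96) = 79%; at .0125 it is Φ(2.78 − 2.50) = 61%. Holm lies between these because later steps are less strict. In simulation at outcome correlation .5, per-scale power is about 70%, and power for at least one scale falls from about 96% to 88%.

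**The case against.** No section says that one scale at .05 is enough. The general claim is a title, not a decision rule. The written hypotheses point elsewhere: Section 2 joins its domains with a conjunction and adds a comparison with baseline, and Section 11 speaks of hypotheses in the plural, which fits a separate claim per scale. The Bonferroni sentence might even have been meant across outcomes. Under these readings the inflation is absent, smaller, or confined to a general claim that would not be made.

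This stands as a limit on the figures. A reader might infer that the plan as written runs at two to four times the nominal error. The documents do not support that, because the multiplier needs a rule they never state. It also depends on assumed correlations, falling to 1.9 at .9.

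It does not remove the gap. The Section 2 hypothesis omits a listed primary outcome and is not framed as a success criterion. Section 11 makes only the group contrast primary. The words limiting Bonferroni to post hoc tests make the across-outcome reading the less natural one.

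A reader might also infer that any correction leaves the trial badly underpowered. On a change-score test with an assumed pre-post correlation of .5, per-scale power is 51% before adjustment and 36% with Holm. That model does not reproduce the plan's 40, and power is already low there before adjustment. That shortfall is a separate sample-size question.

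**Conclusion.** The omission is certain: no section fixes a success rule, an order or an alpha split for the four primary outcomes, and the stated Bonferroni correction does not, on its plain reading, cover them. Its size is conditional. If any one scale may carry the general claim, false improvement is 9.6% to 6.5% rather than 2.5%, for assumed outcome correlations from 0 to .7 and two-sided tests. If all scales must succeed, or alpha was meant to be divided across them, there is no inflation. If each scale is its own claim, each keeps 5% error, but no single result supports the general claim. The plan should be amended so that the choice does not depend on the data.

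**What to change.** State in Section 11 that the between-group comparisons from t0 to t1 (post-intervention in that section's labels) on PHQ-9, WHO-5, PSQ-20 and ISI are tested with Holm at a family-wise two-sided 5%, and that claims are made only for the scales that pass. One named primary outcome or a fixed testing order would also hold 5%.

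Align the Section 2 hypothesis: include well-being, say whether the comparison with baseline is part of the primary claim, and use the same time labels (Section 2 calls the post-intervention visit t2). Section 12 names PSS-10 where the other sections name PSQ-20. Reconcile this so that the stress test is identified; the number of tests does not change.

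The cost is a few sentences and some power, which should be restated in the Synopsis and Section 11.1: on the formula above, per scale from about 79% to 70% (61% for a scale tested at .0125), and for at least one scale from about 96% to 88%. No added enrolment is required if that loss is accepted. Keeping 80% power at .0125 would take about 58 completers per group (2 × (2.498 + 0.842)² × .525 / .45² = 57.8).

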8.7. Early Discontinuation/Withdrawal of Participants

Withdraw is possible at any time and without giving a reason. In case of withdrawal prior randomization, data won't be replaced. In case of withdrawel after randomization, missing data will be estimated by maximum likelihood estimation.

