8.8. Definition of End of Trial

The end of trial is the follow-up measurement.

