11.1. Sample Size Determination

According to the power analysis 40 per group should finish the study per group, in case of 20% drop outs, a minimum of 96 participants should be included.

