12. DATA MANAGEMENT

The whole data collection procedure will be carried out through the ESMira App. ESMira is a tool for running longitudinal studies (ESM, AA, EMA, ...) with completely anonymized communication with participants and data collection. The following validated and frequently used mental health questionnaire will be used: Wellbeing (WHO-5), Depressive Symptoms (PHQ-9), Anxiety (GAD-7), Stress (PSS-10), Sleep quality (ISI), Eating disorder (EAT-8; SCOFF), and body awareness (BAD-2). These questionnaires will be collected at baseline, after intervention and at follow up. During the study, a weekly measurement of well being (WHO-5), body awareness (BAD-2), and stress (PSS-10) will be performed. What is ESMira? It works without a steady internet connection. All functionality of studies are saved locally in the app and saved data are cached and will be uploaded as soon as there is an internet connection. Personal Feedback: Researcher can set up complex charts that will be automatically calculated out of participants' data. These statistics can be either personalised to the participants or calculated out of all participants' data. Completely anonymous: Each participant gets a random participant id under which all data is collected. ESMira does not collect any personal data at any time. Anonymous Chat: Participants can communicate with the researcher from within the app and stay completely anonymous while doing so. Additionally, researchers can send important messages to all participants of a study. Free and open source: ESMira is developed as a project at Karl Landsteiner University to be used for our own studies and published for the community to use completely free of charge. Find out more at: https://github.com/KL-Psychological-Methodology/ESMira

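### As worded, missing scores are filled in by maximum likelihood and then analysed by rm-ANOVA as if observed, so either the standard errors are too small or the effect is diluted

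*Combined protocol and SAP*

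**What the plan says.** Section 11 plans that "repeated measurements ANOVAs (rm-ANOVA) will be applied" to the mental health indicators, with a Greenhouse-Geisser correction where sphericity fails. Its primary comparison is the change from t0 (baseline) to t1 (post-intervention) between the two groups; t2 (follow-up) enters a secondary analysis. These time labels are the ones in section 11 and are used below. On missing data it has one sentence: "Missing values will be estimated with via maximum likelihood estimation".

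Section 8.7 says the same for withdrawal after randomisation: "missing data will be estimated by maximum likelihood estimation". It contrasts this with withdrawal before randomisation, for which nothing is replaced.

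On the expected amount of missing data, section 11.1 says "40 per group should finish the study per group, in case of 20% drop outs, a minimum of 96 participants should be included", and the Synopsis says "Considering a drop-out rate of 20%, at least 50 people per group were recruited". Nowhere do the documents name a mixed model, a direct-likelihood analysis, multiple imputation, the variables used for the estimation, or a correction to the standard errors.

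**The concern.** In both sentences the thing being estimated is the missing value, not a model parameter. Together with a complete-row ANOVA, that describes single imputation: one fitted score per gap, after which the test treats all rows as real data. A filled-in score lies exactly on the regression line and adds no new information, yet it raises the sample size and lowers the apparent variance.

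The consequence depends on a choice that the plan leaves open:

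- **Group in the filling model.** The effect estimate is unbiased, but reported standard errors are too small and false positives rise.
- **Group not in the filling model.** Filled-in scores carry no group difference, so the estimated effect is pulled towards zero while the test keeps its size.

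Only one of these can occur in a given analysis. The trial is unblinded and the choice is not pre-specified, so it could be made after the data are seen.

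**Working it through.** **Inputs from the documents.** Effect d = 0.45, power .80, alpha .05 (taken as two-sided), ICC .05, 40 completers per group, drop-out 20%, and 50 per group (Synopsis) or 96 in total (section 11.1).

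**The plan's own figures.** For two time points with correlation ρ = .05, the normal approximation for the between-group effect is n = 2(1.96 + 0.84)²/0.45² × (1 + ρ)/2 ≈ 77.5 × .525 = 40.7, so 41. With (1 − ρ)/2 for the group × time effect it is 36.8, so 37. The noncentral F versions give 42 and 38. The stated 40 is therefore reproduced to within 2. For recruitment, 40/.8 = 50 per group, whereas 40 × 1.2 = 48 gives the 96. The latter implies 1 − 80/96 = 16.7% drop-out.

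**Assumptions, not in the documents.** Unit SD at t0 and t1; correlation r = .3, .5 or .7; t1 missing completely at random and equally by arm; filling by the conditional mean from t0 only. With n randomised and k observed at t1 per arm, n/k is 50/45 (10% missing), 48/40 (16.7%) or 50/40 (20%). At 20%, 20 of the 200 t0 and t1 scores per 100 participants, or 10%, would be filled in. The primary rm-ANOVA interaction on two time points is the same as a t-test on change.

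**(a) Group in the filling model.** Split the change into the residual part, variance 1 − r², and the part explained by t0, variance (1 − r)². To a close approximation:

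- true SE² = 2[(1 − r²)/k + (1 − r)²/n]
- reported SE² = 2[(k/n)(1 − r²) + (1 − r)²]/n

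At r = .5, n = 50, k = 40:

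- true: 2(.75/40 + .25/50) = .0475, SE .218
- reported: 2(.8 × .75 + .25)/50 = .0340, SE .184
- ratio .846, so type I error ≈ 2[1 − Φ(1.96 × .846)] = .097

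Simulation (20,000 trials per cell) gave .184 against .217 and type I error .098. All cells:

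| t1 missing | Type I error, r = .3 / .5 / .7 | Reported SE too small by |
|---|---|---|
| 10% | .070 / .071 / .075 | 8–9% |
| 16.7% | .083 / .088 / .094 | 12–14% |
| 20% | .093 / .098 / .103 | 14–17% |

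Repeat simulations with separate code agreed to within about .01 on type I error and about one percentage point on the SE shortfall. Adding one random residual to each filled value does not cure the fault: at 20% missing, type I error was .076, .092 and .101 for r = .05, .5 and .7.

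**(b) Group not in the filling model.** The filled fraction contributes no group difference, so the expected estimate is about 0.45 × k/n: 0.405, 0.375 and 0.36 at 10%, 16.7% and 20% missing. Simulation gave 0.41, 0.37 and 0.36, with type I error .048 to .052. Power at 20% missing was .36/.49/.71, against .41/.53/.74 for a likelihood analysis of the observed scores.

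**Benchmark.** The likelihood analysis of the observed scores gave type I error .047 to .052 and an estimate of 0.45.

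**If weekly scores also inform the filling.** Section 12 plans "a weekly measurement of well being (WHO-5), body awareness (BAD-2), and stress (PSS-10) will be performed". With an assumed correlation of .8 between a weekly score and t1, and r = .6, (a) falls to .061/.069/.074 and (b) moves to 0.42/0.41/0.40 at 10/16.7/20% missing.

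**The case against.** **The fault is inferred.** The sentences may be shorthand for a direct-likelihood analysis, and nothing says outright that filled scores enter the ANOVA. This stands as a limit on certainty. It does not rescue the text: under that reading the named model and the Greenhouse-Geisser step are wrong. The contrast in section 8.7 with data that are not replaced also favours the filling-in reading.

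**Which harm applies is unknown, and the power loss in (b) is modest.** Both are true. The harm in (b) is mainly a biased estimate, not a lost test.

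**The missingness at t1 is not given.** The 20% counts people who do not finish the study, and "The end of trial is the follow-up measurement". The post-intervention measurement comes earlier, and the plan has retention measures (a kept fitness tracker, and the intervention offered to controls after follow-up). At 4% missing (2 of 50 per arm), type I error in (a) is only about .052 to .060, and the estimate in (b) is 0.45 × .96 = 0.43. The harm can therefore be small, although the documents do not establish that rate either.

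**The documents' one correlation-like figure is .05.** At r = .05 the type I error in (a) is about .064, .075 and .081 by the formula at 10%, 16.7% and 20% missing. That is lower, but in the same direction.

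**The weekly scores may help little.** They cover only well-being and stress among the primary outcomes, section 12 names PSS-10 while the primary stress outcome is PSQ-20, and people who withdraw may stop the weekly reports too. This limits the mitigation, not the concern.

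**Naming the method would be enough.** Specifying it is the minimum, but if what is then specified is single filling followed by rm-ANOVA, the fault remains.

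**Conclusion.** The concern holds for the text as worded and should be fixed; confidence is medium because single imputation is the plain reading and not an explicit statement. Under that reading, the primary comparison has either a false-positive rate of roughly .07 to .10 in place of .05, or an estimate of 0.36 to 0.41 for a true 0.45, over 10% to 20% of t1 missing. These sizes rest on the assumed correlations of .3 to .7, filling from t0 alone, and missingness completely at random and equal by arm. The direction does not depend on equal missingness: with 10% missing in one arm and 30% in the other (r = .5), type I error in (a) was .093 and the estimate in (b) was 0.35. The harm shrinks as t1 missingness falls.

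**What to change.** Delete the sentences in sections 8.7 and 11 that estimate missing values. Replace rm-ANOVA with a linear mixed model fitted by REML to the observed scores (SPSS MIXED, unstructured covariance), with the t1 group contrast primary and t2 secondary. Give baseline one role only:

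- **Option 1.** t0, t1 and t2 are all responses, and the primary test is the group × time contrast from t0 to t1. This matches the planned comparison and keeps every randomised participant with any score. The section 11 rule on baseline differences must then not also add the same outcome's t0 score as a covariate.
- **Option 2.** t1 and t2 are responses and t0 is a covariate. This is more precise, but participants with no score after t0 leave the model.

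Multiple imputation that includes group, with pooled standard errors, is an acceptable alternative. With the mixed model the Greenhouse-Geisser step is no longer needed; it never affected the two-time-point primary test.

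The cost is a short SAP rewording, with the same software and data. If group would have been in the filling model, intervals become wider but valid. At 20% missing and r = .5, the SE goes from 0.184 to 0.218 under option 1 (apparent power .65 to .53), or to √(2 × .75/40) = 0.194 under option 2 (power .63).
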